4.5.2 Clinical Laboratory Assessments

Hematology, coagulation, serum biochemistry, and urinalysis are collected as scheduled in Table 1 through Table 5. The following information will be derived for each of the hematology, coagulation, serum biochemistry, urinalysis, and other parameters:

- Change from baseline at all post-baseline time points
- Classification relative to the normal range ('Low', 'Normal', or 'High')
- Potentially clinically significant (PCS) abnormalities, if applicable

In addition, the following tests will be performed:

- **Serum Pregnancy Test:** Blood samples to assess pregnancy status by beta-human chronic gonadotropin (β-hCG) will be collected from all female subjects according to the schedules summarized in Table 1 and Table 5.
- Estimated glomerular filtration rate: Estimated glomerular filtration rate (eGFR) will be calculated at the Screening Visit using the 4-variable Modification of Diet in Renal Disease Study (MDRD) equation:
 - eGFR (mL/min/1.73 m²) = 175 × Serum Creatinine $^{-1.154}$ × age $^{-0.203}$ × 1.212 (if participant is black) × 0.742 (if female).
- **Viral Serology**: Blood samples to assess Hepatitis B surface antigen (HBsAg), Hepatitis C virus (HCV) antibodies and human immunodeficiency virus (HIV) antibodies will be obtained at the Screening Visit.
- **Drugs of Abuse and Alcohol Screen:** Urine samples to assess amphetamine, barbiturates, benzodiazepine, cannabinoids, cocaine, ethanol, opiate, oxycodone, methadone and methylenedioxymethamphetamines will be obtained according to the schedule summarized in Table 1.
- **Ketone Bodies:** Blood samples to assess ketone bodies (β-hydroxybutyrate and acetoacetate) will be collected according to the schedules summarized in Table 2 through Table 5.

• Urine Calcium, Sodium and Glucose: Urine samples to assess calcium, sodium and glucose will be collected according to the schedules summarized in Table 1 through Table 4.

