4.5.3 Vital Signs

Vital sign assessments including systolic and diastolic blood pressure, heart rate, respiratory rate and body temperature (°C) will be performed according to schedules summarized in Table 1 through Table 5. The following information will be derived for all vital signs and body weight:

- Change from baseline at all post-baseline time points
- PCS abnormalities

4.5.4 12-Lead Electrocardiogram

12-lead ECG recordings and conduction intervals including interval from beginning of the QRS complex in the frontal plane to the next QRS complex (RR), interval from beginning of the P wave to the beginning of the QRS complex in the frontal plane (PR), duration of QRS complex in the frontal plane (QRS), interval from beginning of the QRS complex to end of the T wave in the frontal plane (QT) and Fridericia-corrected QT interval (QTcF) will be obtained according to the schedules summaried in Table 1 through Table 5. The following information will be derived for each of the 12-lead ECG measurements:

- Change from baseline at all post-baseline time points
- PCS abnormalities

The overall clinical interpretation of an ECG will be assessed as follows: normal, abnormal not clinically-significant or abnormal clinically-significant.

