All subjects randomized to placebo on Day 1 will be included in the placebo treatment group unless otherwise specified.

In the data listings, study day relative to first dose of study drug on Day 1 may be presented. Study day relative to first dose of study drug on Day 1 will be calculated as: event date – first dose date on Day 1 (+ 1 if event date \geq first dose date on Day 1).

Baseline will be the latest non-missing measurement prior to the first dose of study drug on Day 1, unless otherwise specified

For safety summaries, the unscheduled and repeat assessments will not be summarized; however, all results will be included in the data listings.

Disposition, demographics, and baseline characteristics and all categorical safety parameters will be summarized by each treatment group and overall.

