Additionally, the change from baseline (Day -1) of AUEC₀₋₄ will be analyzed using the mixed effect model with repeated measures (MMRM). The model will include fixed effects for treatment, day, and treatment by day interaction, subject as repeated measures and baseline value as a covariate. The difference of the least squares means between each JTT-662 dose group relative to placebo at the same day will be estimated, along with two-sided 90% and 95% CIs and p-values. Least squares means will also be presented.

[figure not shown]
The following sample SAS code may be used, with appropriate changes, for the analysis:

```
PROC MIXED DATA=DATASET;
 CLASS DAY TREATMENT;
 MODEL CHG = DAY TREATMENT DAY*TREATMENT BASELINE / DDFM=KR;
 REPEATED /SUBJECT=SUBJECT(TREATMENT) TYPE=UN*;
 LSMEANS DAY*TREATMENT /PDIFF CL ALPHA=0.1**;
RUN:
```

^{**} alpha = 0.05 and 0.1.

^{*} Other covariance structure will be used if UN leads to non-convergence of the model.

Statistical Analysis Plan - Protocol No. AT662-U-20-003

6.10 **Analysis of Safety Data**

Safety analyses will be conducted on the Safety Population and will be performed for all safety variables specified below.

The safety evaluation will include AEs, clinical safety laboratory tests (e.g., hematology, serum biochemistry, coagulation, urinalysis), vital signs, 12-lead ECGs, BSC findings, ketone bodies, urinary calcium excretion from the time of dosing until the 24-hour time point (UCE₀₋₂₄) and urinary sodium excretion from the time of dosing until the 24-hour time point (UNa E_{0-24}) and UGE $_{0-24}$.

Observed and change from baseline of vital signs, ECG parameters and clinical laboratory data will be presented in tabular form with arithmetic mean, SD, median, minimum and maximum, or in frequency tabulation form as appropriate. For the laboratory safety data, out of range values and PCS abnormalities will be flagged in the data listings.

Potentially clinically significant abnormalities will be defined according to the Akros Safety Reporting Standards Potentially clinically significant values for vital signs, ECG, and laboratory data will be flagged in data listings.

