Treatment-emergent PCS values will be summarized, presenting the number and percentage of subjects who had at least one PCS value after study drug administration on Day 1. The denominator is always the number of subjects in the safety population, regardless of whether the subject had any post-baseline measurements. The numerator is any PCS value in the treatment-emergent period if the baseline is normal or missing; and is any worsening PCS value in the treatment-emergent period if the baseline is also a PCS value.

A worsening PCS is defined as a > (<) 0 change from baseline if a high (low) value indicating undesirable outcome; or the PCS value is in the opposite direction of the baseline PCS value.

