6.10.2 Safety Laboratory Assessments

Observed and change from baseline for each parameter of continuous safety laboratory values (hematology, serum chemistry, coagulation, and urinalysis) will be summarized by treatment group at each time point using descriptive statistics.

Any post-baseline abnormal laboratory finding will be assessed to calculate overall treatment-emergent potentially clinically significant (TEPCS) status as described in tables PCS Criteria for Laboratory Parameters. Values assessed as TEPCS will be summarized categorically per treatment group and overall.

A listing of all safety laboratory data for each subject at each time point will be presented. Out of range values and PCS values will be flagged in the data listing. Safety laboratory values that are outside the normal ranges will be presented in a separate listing together with normal ranges values. For the listing presenting all abnormal values, if a subject has any abnormal value for a test, all values of that test of the subject will be presented.

Statistical Analysis Plan - Protocol No. AT662-U-20-003

Qualitative urine parameters are generally reported by a descriptive score, which may differ between laboratories. For pooling the data, a four-point scale is used. A clinical review will be performed on the mapping of the descriptive scores to the four-point scale; and the descriptive scores will be remapped where appropriate. The four-point scale will be used in the summary of the PCS abnormality analysis.

Five-point scale	Four-point scale
Negative	Negative
Trace	Rare/Mild
1+	Rare/Mild
2+	Moderate
3+	Severe

The mean profile by treatment group will be presented for selected laboratory parameters.

If the non-numeric result is reported for quantitative laboratory parameter then for summary and analysis it will be changed as follows into numerical value:

- a) If less than '<' sign is used then the value will be reduced by 1 point from the last precision digit
- b) If greater than '>' sign is used then 1 point will be added to the last precision digit.

Eg: if the laboratory parameter is reported to 2 decimal precision, <40.01 then for summary and analysis it will be treated as 40.00, if laboratory parameter is reported as whole number >40 then it will be considered as 41 and if the parameter is reported with 1 decimal precision <40.1 then it will be considered as 40.0.

Potentially Clinically Significant Criteria for Laboratory Parameters

Hematology

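### SAP 6 excludes unscheduled and repeat values from all safety summaries, which conflicts with SAP 6.10's count of subjects with any treatment-emergent PCS value; the baseline wording in 6.10 also needs clarifying

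*SAP*

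**What the plan says.** The general rule is in SAP 6 (Statistical Methods): "For safety summaries, the unscheduled and repeat assessments will not be summarized; however, all results will be included in the data listings". It names no exception.

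SAP 6.10 (Analysis of Safety Data) defines the TEPCS table as "presenting the number and percentage of subjects who had at least one PCS value after study drug administration on Day 1", with the safety population as denominator. SAP 6.10.2 begins its laboratory rule with "Any post-baseline abnormal laboratory finding will be assessed to calculate overall" TEPCS status. SAP 6.10.3 and 6.10.4 use the same any-post-baseline wording for vital signs and ECG.

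The numerator in SAP 6.10 has two branches. The first reads "The numerator is any PCS value in the treatment-emergent period if the baseline is normal or missing". The second applies when the baseline is itself PCS, and then only a worsening PCS value counts. For laboratory data, SAP 4.5.2 classifies each result as low, normal or high against its reference range and derives PCS status as a separate item. On the limits, the SAP says "Potentially clinically significant abnormalities will be defined according to the Akros Safety Reporting Standards"; the limits are not visible in the public text.

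Protocol 3.6.7 allows additional safety tests when the Investigator thinks them necessary. SAP 3.4 states that the Investigator and site staff are unblinded.

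**The concern.** The TEPCS table is a safety summary, so the SAP 6 exclusion covers it on its plain wording. Its own definition is an ever-occurrence count: did the subject have a PCS value at any time after the Day 1 dose? An exclusion of unscheduled and repeat values suits means and changes at fixed time points, where extra values would distort the visit statistics. It does not suit an ever-occurrence count, because an unscheduled test is often ordered when something looks wrong. The rule could therefore leave out values the table exists to count.

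Safety and tolerability is the first-listed objective. Two programmers working from this text, one following SAP 6 and the other SAP 6.10, could produce different tables.

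The baseline wording is a lesser worry. If *normal* means within the reference range, a subject whose laboratory baseline is low or high, but short of PCS, fits neither branch.

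**Working it through.** The documents give no figure for this point, so there is nothing to reproduce. The check compares the two rules and then asks what the documents allow to be said about size.

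**1. The two rules on one case.** Take a subject with a within-range baseline for a test, no PCS value at any scheduled post-dose time, and one PCS value from an unscheduled sample after the Day 1 dose.

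| Rule applied | Subject counted in the TEPCS table? |
|---|---|
| SAP 6.10 and 6.10.2 (at least one PCS value; any post-baseline finding) | Yes |
| SAP 6 (unscheduled and repeat values not summarized) | No |
| Listings (SAP 6 and 6.10) | Value shown and flagged |

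A PCS value seen only on a repeat gives the same result.

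**2. Direction.** With baseline fixed, removing values from an at-least-one count can lower it or leave it unchanged, never raise it. The shortfall equals the number of subjects who qualify only through an unscheduled or repeat value. How it falls between JTT-662 and placebo depends on who receives extra tests, which the documents do not predict.

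**3. Where it can matter.** It matters only when no scheduled value of that parameter qualifies. Scheduled post-dose assessments per completer, from Tables 2 to 5:
- Biochemistry: Days 2, 7, 10, 14, 19, 24, 28, 31, 35, 42 = 10.
- Coagulation: the same days without Day 2 = 9.
- Vital signs, and likewise ECG: Day 1 (3) + Day 2 (2) + Days 7 and 10 (4) + Day 14 (4) + Days 19 and 24 (4) + Day 28 (4) + Days 31, 35 and 42 (3) = 24.

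Laboratory tests have fewer scheduled chances, so this is mainly a laboratory issue.

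**4. Weight of one subject.** SAP 6.1 gives 9 active and 3 placebo in each of 3 cohorts, and SAP 6 pools placebo: 3 × 3 = 9. One subject is 1/9 = 11.1 percentage points and two are 2/9 = 22.2. These are the weights of one or two subjects in any table with groups of 9, not estimates of this effect. The number affected cannot be derived, because the documents give no PCS limits, reference ranges or frequencies.

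**5. The baseline branches.** For a post-dose PCS value that is worse than baseline:

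| Baseline | *Normal* = within range | *Normal* = not PCS |
|---|---|---|
| Within range | Counted | Counted |
| Missing | Counted | Counted |
| PCS | Counted | Counted |
| Out of range, not PCS | No rule | Counted |

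One state of four depends on the reading. Eligibility does not rule it out. Protocol 3.3.1 exempts glucose-related results from the acceptability criterion and allows fasting glucose up to 280 mg/dL. Protocol 3.3.2 excludes ALT or AST only above 2.0 × ULN. Whether such values fall short of PCS cannot be checked without the limits.

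**The case against.** **The general rule may be meant to govern.** The word *any* in 6.10 and its subsections can be read within SAP 6, so that the table covers scheduled values only. That is coherent and has a rationale: unblinded staff decide when to order extra tests, so counting them lets the rates partly reflect how closely each group is watched. This stands as an argument for a scheduled-only table. It does not stand as a defense of the text, because SAP 6.10 describes a different table and nothing says which sentence prevails.

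**The visible text favors *not PCS*.** One numerator rule serves laboratory, vital-sign and ECG data, yet the low/normal/high classification is given only for laboratory data. The second branch, for a baseline that is also PCS, suggests that the first is its complement. SAP 4.5.4 does separate normal from abnormal but not clinically significant ("The overall clinical interpretation of an ECG will be assessed as follows: normal, abnormal not clinically-significant or abnormal clinically-significant"), but only for the overall ECG reading. SAP 6.10.2 also refers the derivation to criteria tables whose limits are not visible, and these may settle the matter. Most of this stands, so the baseline point is a likely wording slip, not a proven error.

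**Little depends on the table.** No formal inferential test is planned, the suspension criteria in Protocol 3.5 rest on adverse events, and every result is listed. This stands and limits the severity. Adverse event reporting is only a partial backstop: Protocol 3.7.1 asks for symptoms, permanent discontinuation of study drug or a change in concomitant therapy, and generally exempts findings associated with the disease under study.

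**Conclusion.** A minor point, held with moderate confidence. SAP 6 and SAP 6.10 conflict on whether unscheduled and repeat values count toward TEPCS. Followed literally, SAP 6 can only lower the count in a first-objective safety table. The total effect and its direction between groups cannot be computed. The baseline wording is secondary: on one reading it leaves a laboratory state without a rule, but *not PCS* is probably intended. The unseen PCS limits are not themselves a fault of the plan.

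Three stronger inferences are tempting, and the documents do not support them:
- *Unscheduled PCS values are lost.* They are not: all results are listed and PCS values are flagged. The laboratory listing of abnormal values also shows every value of a test for any subject with one abnormal value, so most laboratory cases can be recovered by hand.
- *Baseline is undefined when there is a pre-dose repeat.* SAP 6 says "Baseline will be the latest non-missing measurement prior to the first dose of study drug on Day 1, unless otherwise specified", which on its face includes a repeat. The exclusion concerns what is summarized.
- *Early-discontinuation assessments drop out as unscheduled.* Protocol 3.4 and 3.6.4 ask these subjects to undergo the Day 35 procedures, so these are protocol-specified assessments.

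**What to change.** Make three wording changes before database lock:

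1. In SAP 6, limit the exclusion of unscheduled and repeat assessments to descriptive statistics by time point.
2. In SAP 6.10, state that all values after the Day 1 dose, including unscheduled and repeat values, count toward TEPCS. Add a footnote giving, by group, the number of subjects who qualify only through an unscheduled or repeat value.
3. In the first numerator branch of SAP 6.10, replace *normal* with *not PCS*, whether in or out of range, and keep the worsening branch as it is. If the sponsor's criteria already say this, a cross-reference is enough.

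The cost is a few sentences and a small derivation change, with no new data. The drawback is that unblinded staff order the extra tests, so the rates may partly reflect testing frequency. The footnote makes that visible and lets a reader recover the scheduled-only count. If the sponsor prefers scheduled values only for this reason, SAP 6.10 should say so and describe the table accordingly.

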6.10.1 Adverse Events

Adverse events will be coded using the MedDRA (Version 23.0) and will be summarized by SOC and PT.

A treatment-emergent adverse event (TEAE) is defined as any AE with an onset date/time at or after the placebo dosing on Day -1. A pre-treatment AE is defined as any AE with an onset date before the placebo dosing on Day -1.

The summary of TEAEs will be presented for the following groups:

- Placebo run-in: including AEs with onset between the placebo dosing on Day -1 and before dosing on Day 1 for all subjects in the safety population.
- Placebo treatment group: including AEs with onset at or after the placebo dosing on Day 1 for the subjects who are randomized to placebo on Day 1.
- JTT-662 5 mg: including AEs with onset at or after the JTT-662 5 mg dosing on Day 1 for the subjects who are randomized to JTT-662 5 mg on Day 1.

- JTT-662 10 mg: including AEs with onset at or after the JTT-662 10 mg dosing on Day 1 for the subjects who are randomized to JTT-662 10 mg on Day 1.
- JTT-662 XX mg (XX represents JTT-662 dose level for Cohort 3): including AEs with onset at or after the JTT-662 XX mg dosing on Day 1 for the subjects who are randomized to JTT-662 XX mg on Day 1.

The overall incidence of TEAEs (number and percentage of subjects) as well as the number of events will be summarized for each treatment group.

Summaries of TEAEs will include the following: Incidence of TEAEs (overview including number and percentage of participants with any TEAEs, serious TEAEs, discontinuations due to TEAEs, drug-related TEAEs, severe TEAEs, all deaths (AEs leading to death regardless of treatment emergence) and TEAEs leading to death; event counts will also be included).

The TEAEs will be summarized by SOC, PT, and treatment group using frequency counts and percentages (number and percentage of subjects with an event). Each subject may only contribute once to each of the incidence rates, regardless of the number of occurrences. In addition, the following summaries will be performed for the summary groups as described above:

- TEAEs by SOC, PT
- TEAEs by SOC, PT and maximum reported severity
- TEAEs by SOC, PT and causality
- TEAEs by PT (in order of descending frequency in the total JTT-662 group).
- Serious Adverse Events (SAE) by SOC, and PT

Listings of AEs, SAEs, AEs leading to study discontinuation will also be presented. The AEs with onset in the placebo run-in period will be flagged in the listings.

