#### Start Date and Time, and End Date and Time of Adverse Event:

The start date and time of each AE with an onset time during the period for AE assessment should be recorded. The end date and time of each AE should be recorded in the following manner:

- If the outcome of AE is "Recovered/Resolved" or "Recovered/Resolved with Sequelae", record the date and time of the AE outcome.
- If the outcome of AE is "Fatal," record the date of the death.
- If the outcome of AE is "Recovering/Resolving" or "Not recovered/Not resolved", the end date and time of the AE outcome should NOT be recorded.

For AEs related to abnormalities in parameters such as vital signs, ECGs, record the date/time when the test was performed as the start date/time and end date/time. For AEs related to abnormalities in laboratory values, record the date/time when the sample was collected for the test as the start date/time and end date/time.

If an identical AE occurs repeatedly in a subject, the Investigator (or designee) should judge whether it is a single event or a composite of more than one event considering the features, frequency and severity of the AE from a medical perspective.

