4.5 Safety Parameters

4.5.1 Adverse Events

Adverse events occurring (initial occurrence or a worsening of a pre-existing condition) after the ICF has been signed and up to the day when the decision to screen fail the subject is made (for screen failure subjects), up to 7 days (for subjects discontinuing the study after dosing on Day -1, but before dosing on Day 1) or 14 days (for subjects discontinuing the study after dosing on Day 1) after the last dose of study drug will be reported and entered in the case report forms (CRFs).

The Medical Dictionary for Regulatory Activities (MedDRA) Version 23.0 will be used to map verbatim AEs to preferred term (PT) and their respective primary system organ class (SOC). However, a different (non-primary) system organ class may be selected where appropriate after a medical review of the mapping.

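### The SAP's treatment-emergent rule has no worsening clause, so an AE that starts before Day 1 dosing, worsens on JTT-662 and stays one record can be left out of the JTT-662 tables

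*SAP*

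**What the plan says.** SAP 6.10.1 defines a treatment-emergent event as one "defined as any AE with an onset date/time at or after the placebo dosing on Day -1". The complement is also set by onset: "A pre-treatment AE is defined as any AE with an onset date before the placebo dosing on Day -1". TEAEs are then placed in columns. The run-in column is described as "including AEs with onset between the placebo dosing on Day -1 and before dosing on Day 1". The 5 mg column is described as "including AEs with onset at or after the JTT-662 5 mg dosing on Day 1", for subjects randomised to that dose, and the other dose columns and the placebo column follow the same pattern. Tables by maximum severity and by causality use these columns. On visibility, the section adds: "The AEs with onset in the placebo run-in period will be flagged in the listings".

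The collection rules are wider. SAP 4.5.1 takes in both "initial occurrence or a worsening of a pre-existing condition", and Protocol 3.7.1 and 3.7.3 likewise treat worsening after consent as an adverse event. Protocol 3.7.2 adds: "If an identical AE occurs repeatedly in a subject, the Investigator (or designee) should judge whether it is a single event" or several, and names severity among the factors to weigh.

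For potentially clinically significant (PCS) laboratory, vital sign and ECG values, SAP 6.10 does have a worsening provision. The numerator "is any worsening PCS value in the treatment-emergent period if the baseline is also a PCS value".

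**The concern.** Worsening makes something an adverse event at collection, but it plays no part in deciding treatment emergence or column at analysis. The two rules fit together only if every worsening gets its own dated record, and neither document requires that for an event that is already open. Protocol 3.7.2 describes one start, one severity grade and one outcome per event, and leaves the single-or-multiple judgement on repeated events to the Investigator. Under Protocol 3.8.8 the Investigator knows the treatment. A recording choice made with that knowledge can therefore decide whether an event counts against the drug.

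Safety and tolerability is the first-listed objective. Protocol 1.1.3 links loss of SGLT1 function to watery diarrhoea, so worsening of an existing bowel symptom is a plausible drug effect. Exclusions 14 and 15 remove only subjects with a general pattern of two or more Type 6 or 7 stools a day, so milder symptoms can be present at entry.

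**Working it through.** The plan states no figure to reproduce, since the sample size is not statistically determined. The check follows an event through the rules.

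**Period in which an affected event can start.** Screening runs from Day -31 to Day -4 (28 days), and Days -3 to -1 follow (3 days). That gives 28 + 3 = 31 days at most, depending on when consent is signed.

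**Where SAP 6.10.1 places an event that worsens on JTT-662.**

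| First onset | How the worsening is recorded | Where it is tabulated |
|---|---|---|
| After consent, before the Day -1 placebo dose | Same record | Pre-treatment: no TEAE table |
| From the Day -1 placebo dose to before the Day 1 dose | Same record | Placebo run-in, at maximum severity |
| Either of these windows | New record dated at the worsening | JTT-662 column |
| Condition present before Day 1 dosing and classed as medical history | Entered as an AE on worsening | JTT-662 column |

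The first two rows are the gap. The last two are counted correctly.

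**The medical-history route.** Its cutoff is not consistent. Protocol 3.6.7.5 ends the judgement on Day -1 before placebo, whereas Protocol 3.7.3 and SAP 4.1.2 end it on Day 1 before dosing. Whether a condition first seen in run-in can take this route depends on which section is followed.

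**Direction.** Events with onset or worsening after Day 1 dosing include all events with onset after it. For any randomised column, the present rule therefore gives a count equal to or lower than a rule with a worsening clause.

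**Scale of one subject.** Each dose group has 9 subjects, and JTT-662 has 3 × 9 = 27. One subject is 1/9 = 11.1 percentage points, or 1/27 = 3.7 points. Pooled placebo has 3 × 3 = 9, so one subject there is also 11.1 points. SAP 6.10.1 counts each subject once per incidence rate, so these figures apply only where the subject is not already counted in that row.

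**Chance of at least one affected subject.** This rests on an assumption outside the documents: a share q of subjects has an event that starts before Day 1 dosing, worsens on JTT-662 and stays one record. The chance is 1 − (1 − q)^n.

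| q (assumed) | n = 9 | n = 27 |
|---|---|---|
| 2% | 17% | 42% |
| 5% | 37% | 75% |
| 10% | 61% | 94% |
| 20% | 87% | 99.8% |

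These values show sensitivity to q. They do not estimate it.

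**The case against.** The strongest reply is that worsening is handled at collection. A worsened condition is itself reportable and each event has its own start, so a worsening entered after Day 1 dosing falls in the JTT-662 column without any change to the SAP. The repeated-event rule makes severity a factor and does not tell sites to merge a worse episode into a milder one. Subjects have been on stable metformin for at least 12 weeks before screening, so bowel symptoms from it would mostly predate consent and be medical history. Stool types, including the highest type after treatment, are summarised by treatment group regardless of TEAE status.

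Most of this stands, and it rules out three stronger readings that a reader might infer:

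- **That a worsening event is never counted against JTT-662.** It is missed only if it remains one record with its first onset.
- **That the column depends on onset alone.** It depends on the onset window and the randomised arm.
- **That the AE and PCS rules contradict each other.** PCS values are repeated measurements compared with a baseline, while AEs are event records, so a different rule is not in itself an error.

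Other safeguards limit the harm. All AEs are listed, run-in events are flagged, deaths are counted whatever their treatment-emergent status, and the suspension criteria in Protocol 3.5 rest on relatedness to JTT-662.

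What the reply does not supply is any text requiring a new record when an open event worsens. The listings and stool summaries also leave the TEAE incidence, severity, causality and discontinuation tables uncorrected.

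**Conclusion.** The point holds in limited form. SAP 6.10.1 is a stated rule that can misattribute an event, beyond simply leaving a detail unspecified. A single-record event that starts before Day 1 dosing and worsens on JTT-662 is either absent from the TEAE tables or shown under placebo run-in at its maximum severity.

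The effect on any randomised column is a possible undercount. Its effect on the JTT-662 versus placebo comparison is less certain, because the same rule applies to the placebo column. The comparison is understated only if such worsening is more common on drug. The number of affected events is unknown. The conclusion assumes that at least some sites or staff would keep a worsening event as one record, which the documents permit but do not direct.

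The change is worth making before the tables are produced. It is not a threat to subject safety monitoring during the trial.

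**What to change.** In SAP 6.10.1, define a TEAE as an AE with onset at or after the Day -1 placebo dose, or with earlier onset and an increase in severity or seriousness after that dose. Count an AE that worsens at or after Day 1 dosing in the subject's randomised group, at its severity after Day 1 dosing. Apply this equally to placebo and JTT-662.

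Use one mechanism only, so that an episode is not counted twice in the randomised group's event counts:

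- **New record.** Instruct the site to open a new dated AE record at each severity increase. The existing onset rule then places it correctly.
- **Reassignment.** Keep one record and move it in the analysis. This needs the date of the increase to be collected, which the single start and single grade described in Protocol 3.7.2 do not provide.

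Also reconcile the medical-history cutoff between Protocol 3.6.7.5, Protocol 3.7.3 and SAP 4.1.2.

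The cost is SAP wording and a CRF completion instruction or an added date field. The downside is slightly higher TEAE counts in the randomised columns.
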